OBJECTIVES	
Primary Objective: Determine if perioperative vaccination with CV301 in combination with nivolumab, systemic chemotherapy and surgical resection improves 3 year OS as compared to perioperative nivolumab, systemic chemotherapy and surgical resection in patients with hepatic-limited metastatic colorectal cancer. Overall survival is defined as time from metastasectomy to date of death from any cause.
 
Secondary Objectives:
 
• Compare 3-year recurrence-free survival (RFS) between the experimental and control treatment groups.• Compare 3-year OS between the experimental and control groups• Compare OS (in the experimental and control groups) to historical controls• Evaluate the best overall response rates (both by RECIST 1.1 and surgical pathology) between the experimental and control groups.• Compare the pathologic complete response rate to neoadjuvant therapy in resected tumor tissue between the experimental and control groups.• In patients who experience a recurrence after surgery, evaluate the proportion of patients amenable to complete re-resection/ablation between the experimental and control treatment groups.• In patients who experience a recurrence after protocol therapy, compare the progression free survival post-recurrence between the experimental and control groups.• Evaluate the perioperative surgical outcomes (complications and severity scores) between the experimental and control groups.• Compare 3-year OS from the date of registration between the experimental and control 
Exploratory Objectives: Analyze the following laboratory experiments for biomarker analyses and correlate with response to therapy and clinical outcomes:
 
• mRNA signature in tumor tissue pre- and post-therapy by whole transcriptome sequencing using RNAseq

	
• Genomic profiling of metastatic and primary tumor DNA• CEA and MUC-1 antigen-specific immune response in pre- and post-therapy peripheral blood by intracellular cytokine staining and/or ELISPOT or other validated assays.• Other tumor-associated antigen-specific immune response measures may be assessed if adequate samples are available• TCR clonality assays• Serum cytokine, and serum soluble factors• PD-1/PD-L1 staining in pre- and post-therapy tumor tissue.• Immunoscore by IHC
STUDY DESIGN	
This is a multi-center Phase II randomized study. We plan to enroll 78 patients with biopsy-proven hepatic-limited metastatic colorectal cancer deemed resectable after multi-disciplinary discussion. Eligible patients must have confirmed isolated liver metastases by radiographic imaging of the investigators' choosing. Imaging must include the chest, abdomen, and pelvis regardless of imaging modality chosen. Patients will be randomized to either the control arm or the experimental arm. The control arm will receive mFOLFOX6 every 2 weeks for 4 cycles concurrently with Nivolumab. The experimental arm will first be treated with 2 vaccinations of MVA-BN-CV301 given two weeks apart (Days -28, -14) concurrently with Nivolumab followed by 4 vaccinations of FPV-CV301 given two weeks apart concurrently with mFOLFOX6 and Nivolumab, which will again be administered every 2 weeks for 4 cycles (FPV-CV301, mFOLFOX6 and Nivolumab) After Cycle 4, patients will be re-evaluated for surgical resection by re-staging CT chest, abdomen and pelvis (C/A/P). Patients still considered resectable will undergo surgical resection with the goal of complete resection. Patients who cannot be completely resected will continue to be followed on study, and an additional appropriate candidate will be randomized to the corresponding arm.
 
We will collect peripheral blood and tumor tissue at the time of surgical resection, if applicable, or by re-biopsy if resection is not possible. Post-operative therapy will begin when patients are deemed ready by their surgical oncologist team. Patients in the control arm will then undergo another 8 cycles of mFOLFOX6 with Nivolumab administered concurrently. Nivolumab will then be administered every four weeks. The experimental arm will receive the same post-operative regimen but including FPV-CV301 boosters given concurrently with mFOLFOX6 and Nivolumab. FPV-CV301 will then be administered every 12 weeks, and Nivolumab every 4 weeks. We will collect peripheral blood for evaluation of correlates upon the completion of therapy. The vaccination approach of initial immunization during the neoadjuvant period followed by FPV-CV301 boosters for two years postoperatively was chosen to optimize the induction of a long-lasting tumor-specific host response.

	
Neoadjuvant vaccination will also allow for analysis of the tumor microenvironment in resection specimens.
 
Post-therapy patients will be under surveillance per NCCN guidelines with repeat CEA every 3 months for 2 years followed by every 6 months for 1 year (total 3 years), repeat CT of the C/A/P every 3 months for 2 years followed by every 6 months for up to 1 year (total 3 years), and colonoscopy at one year with repetition based on findings at the time of the procedure.

KEY ELIGIBILITY CRITERIA (See Section 3 for full eligibility)	
Inclusion Criteria
 
1. ECOG Performance Status of ≤ 2 and/or sufficient to undergo both perioperative systemic chemotherapy and hepatic surgery as determined by surgical and medical oncology evaluations.2. Histologically confirmed hepatic-limited metastatic colorectal cancer.3. Genomic testing results are required. FoundationOne platform is preferred, however results from an equivalent genomic platform may be used after discussion with the sponsor investigator.4. Completely resectable disease as determined by the guidelines below and surgical oncology evaluation. Patients with bilobar disease that requires resection and ablation are allowed provided the surgical oncologist can render the patient NED (no evidence of disease) at the conclusion of the operation. Synchronous primary colorectal and metastatic hepatic tumors are eligible, provided all disease can be resected in a single operation. NOTE: Subjects who had surgery for their primary tumor prior to registration to this trial are still eligible.5. No radiographic evidence of involvement of: extrahepatic bile ducts, main portal vein or celiac/retroperitoneal lymph nodes.6. Adequate predicted functional liver remnant (FLR) as measured by CT and 3D CT volumetry as deemed by the individual site surgical oncologists.7. Patients must be treatment naïve with respect to their stage IV colorectal cancer. History of prior adjuvant systemic chemotherapy containing oxaliplatin is allowed as long as it has been greater than 12 months from completion of oxaliplatin to study enrollment. NOTE: Neoadjuvant pelvic chemoradiotherapy as part of the management of synchronous metastatic rectal cancer is allowed, provided chemoradiation was completed prior to enrollment on study.8. Demonstrate adequate organ function. All screening labs must be obtained within 28 days prior to registration.9. Females of childbearing potential must have a negative serum pregnancy test within 24 hours of study drug.10. Females of childbearing potential and males must be willing to abstain from heterosexual intercourse or to use contraception as outlined in Section 5.6

11. As determined by the enrolling physician or protocol designee, ability of the subject to understand and comply with study procedures for the entire length of the study.

Exclusion Criteria

1. Patients with mutations in or deficient expression of one or more of the mismatch repair genes listed: MSH2, MSH3, MSH6, MLH1, PMS1, PMS2.
2. Active infection requiring systemic therapy.
3. Pregnant or breastfeeding (**NOTE:** breast milk cannot be stored for future use while the mother is being treated on study).
4. Second primary malignancy within the last 2 years. Clear exceptions are 1) patient had a second primary malignancy but has been treated and disease free for at least 2 years or is considered likely to be cured by their oncologist if the period has been less than 2 years, 2) in situ carcinoma (e.g. in situ carcinoma of the cervix, basal or squamous cell skin cancer, and superficial bladder cancer). Patients with chronic lymphocytic leukemia will be allowed if their blood counts are within acceptable hematologic parameters and if they are not currently requiring cytotoxic or biologic anticancer treatment (supportive treatment such as IVIG is permitted).
5. Metastatic disease not limited to the liver. Disease not amenable to complete resection, not resectable within the confines of a single surgery, or where resection would result in inadequate functional liver remnant.
6. Has a known history of immunodeficiency including but not limited to patients with HIV/AIDS and chronic Hepatitis B/C. Testing is not required.
7. Patient with clinically significant cardiomyopathy, coronary disease, heart failure New York Heart Association (NYHA) class III or IV, or cerebrovascular accident (CVA) within 1 year of study enrollment (CV301).
8. Subjects with known severe allergy to eggs, egg products, or aminoglycoside antibiotics (for example, gentamicin or tobramycin) (CV301).
9. Participants with an active, known or suspected autoimmune disease. Participants with type I diabetes mellitus, hypothyroidism only requiring hormone replacement, skin disorders (such as vitiligo, psoriasis, or alopecia) not requiring systemic treatment, or conditions not expected to recur in the absence of an external trigger are permitted to enroll.
10. Participants with a condition requiring systemic treatment with either corticosteroids (> 10 mg daily prednisone equivalent) or other immunosuppressive medications within 14 days of start of study treatment. Inhaled or topical steroids, and adrenal replacement steroid

	
doses > 10 mg daily prednisone equivalent, are permitted in the absence of active autoimmune disease.
 
11. Participants with history of life-threatening toxicity related to prior immune therapy (e.g. anti-CTLA-4 or anti-PD-1/PD-L1 treatment or any other antibody or drug specifically targeting T-cell co-stimulation or immune checkpoint pathways) except those that are unlikely to reoccur with standard countermeasures (e.g. Hormone replacement after adrenal crisis)
 
12. Patients with serious or uncontrolled medical disorders.
 
13. Treatment with botanical preparations (e.g. herbal supplements or traditional Chinese medicines) intended for general health support or to treat the disease under study within 2 weeks prior to randomization/treatment.
 
14. History of allergy or hypersensitivity to study drug components.
 
15. Has received a live vaccine within 30 days of the planned start of study therapy. Note: seasonal flu vaccines for injection are generally inactivated vaccines and are allowed, however intranasal influenza vaccines are live attenuated vaccines and are not allowed.
 
16. History of allogenic stem cell or solid organ transplant.

STATISTICAL CONSIDERATIONS	
This is a phase II randomized (1:1) clinical trial comparing the control group receiving standard of care perioperative chemotherapy, nivolumab and surgery to the experimental group receiving perioperative chemotherapy, nivolumab in combination with the CV-301 vaccine.
 
Based on a study by Morse et al.¹, the survival probability of the control group at 3 years is 0.588. With a sample size of 70 resected patients (35 per study arm), we will have 80% power to detect an increase in the 3-year OS rate from 58.8% to 88.7% using a 2.5% level one-sided log-rank test. Note that the 3-year survival rate of the vaccine treated cohort in the study by Morse et. al. was 92.5%. We will enroll 74 patients, with the expectation that about 5% of the patients will not go on to resection due to either disease progression or complications of neoadjuvant therapy [2], leaving us with approximately 70 resectable patients. If the number of unresectable patients is higher than 5%, then we will enroll up to 78 patients.
 
An analysis is planned at 2.5 years. The purpose of this analysis is allow an early assessment of efficacy.

TOTAL NUMBER OF SUBJECTS	N = 78 patients
ESTIMATED ENROLLMENT PERIOD	Estimated 12 months

ESTIMATED STUDY DURATION	Estimated 60 months

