4. SUBJECT REGISTRATION

This protocol is open to both men and women and all races. All subjects must be registered through HCRN's electronic data capture (EDC) system. A subject is considered registered when an "On Study" date is entered into the EDC system. Subjects must be registered and randomized prior to starting protocol therapy. Subjects must begin therapy **within 5 business days** of randomization.

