4.1 Randomization

1:1 randomization with no stratification.

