5.1.2 Neoadjuvant Therapy

Patients who are eligible for and consent to enroll onto this trial will be randomized to either the control arm or the experimental arm. One cycle is 2 weeks.

- Patients in the control arm (Arm A) will receive mFOLFOX6 and Nivolumab given on Day 1 of every 2 week cycle for 4 cycles (Cycle 1 - Cycle 4). The treatment order for Arm A is Nivolumab followed by mFOLFOX6.
- The experimental arm (Arm B) will receive two doses of Nivolumab and MVA-CV301 each given Days -28, -14, followed by four cycles of Nivolumab plus FPV-CV301 given on Day 1 of every 2 week cycle concurrently with mFOLFOX6, which will again be administered every 2 weeks for 4 cycles (Cycle 1 – Cycle 4). For Arm B the order of administration is Nivolumab followed by the vaccination at least one hour prior to mFOLFOX6.

A window of +2 days between administration of Nivolumab +/- vaccination and mFOLFOX6 is allowed. This window will accommodate subjects that receive their chemotherapy locally. If there is more than a 2-day delay for any reason, administration of study drugs should be re-aligned so that the chemotherapy falls within +2 days with the next cycle.

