12. STATISTICAL METHODS

12.1 Study Design

This is a multi-center, 1:1 randomized clinical trial comparing CV-301 vaccine to standard treatment in patients with resectable hepatic metastatic colorectal cancer.

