12.3 Sample Size and Accrual

This is a 1:1 randomized clinical trial comparing CV-301 vaccine to standard treatment in patients with resectable hepatic metastatic colorectal cancer. Based on a study by Morse et al. [17], the OS probability at 3 years is 0.588. We would like to detect an increase in OS in the CV-301 study arm with 80% power, using a 2.5% level one-sided log-rank test. This survival analysis will be from the time of metastasectomy.

With a sample size of 70 resected patients (35 per study arm), we will have 80% power to detect an increase in the 3-year OS rate from 58.8% to 88.7% using a 2.5% level one-sided log-rank test. Note that the 3-year survival rate of the vaccine treated cohort in the study by Morse et. al. was 92.5%. We will enroll 74 patients, with the expectation that about 5% of the patients will not go on to resection due to either disease progression or complications of neoadjuvant therapy³, leaving us with approximately 70 resectable patients. If the number of unresectable patients is higher than 5%, then we will enroll up to 78 patients.

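### Read as written, one synopsis clause sends the replacement for an unresected patient to that patient's arm, which contradicts the 1:1 randomisation stated everywhere else

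*Combined protocol and SAP*

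**What the plan says.** The Study Design part of the synopsis covers patients whose disease cannot be completely resected after neoadjuvant treatment. They stay in follow-up, and "an additional appropriate candidate will be randomized to the corresponding arm". The only arm to which the new patient can correspond is that of the unresected patient.

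The other statements on allocation carry no such qualification:
- Section 4.1 says only: "1:1 randomization with no stratification".
- Section 4 says "All subjects must be registered through HCRN's electronic data capture (EDC) system" and requires each subject to be randomised before treatment starts.
- Section 12.1 says "This is a multi-center, 1:1 randomized clinical trial comparing CV-301 vaccine to standard treatment", and Section 12.3 repeats the 1:1 description.
- The synopsis, under Statistical Considerations, says "This is a phase II randomized (1:1) clinical trial comparing the control group".

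For non-resection, Section 12.3 and the synopsis statistical section use a different device. They plan 74 patients on the expectation that about 5% will not be resected, and then: "If the number of unresectable patients is higher than 5%, then we will enroll up to 78 patients". Section 5.1.3, which describes what happens to unresectable patients, has no replacement rule.

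**The concern.** A patient sent to a named arm is not randomised, so the clause contradicts itself as well as Section 4.1. What sets the arm is another patient's post-randomisation event.

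The possible harm is to allocation concealment. A site knows which arm its own unresected patient was in, because the arms differ visibly ("The experimental arm (Arm B) will receive two doses of Nivolumab and MVA-CV301 each given Days -28, -14") and no masking is described. If the site also knew that its next patient would fill that slot, it could choose whom to offer. Directed patients who are then resected would enter the primary log-rank comparison, since Sections 12.6 and 12.7 analyse resected patients.

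The clause may be there to protect the design figure in Section 12.3: "With a sample size of 70 resected patients (35 per study arm), we will have 80% power". The working therefore also asks what an exact 35/35 split is worth.

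**Working it through.** **The plan's own figures.** Section 12.3 gives 70 resected patients, about 5% non-resection, 3-year OS of 58.8% against 88.7%, and a one-sided 2.5% log-rank test.
- Enrolment: 70 / 0.95 = 73.7, rounded up to 74; 74 × 0.95 = 70.3. This reproduces.
- Power at 35 per arm: hazard ratio = ln(0.887) / ln(0.588) = 0.226. The Lachin–Foulkes formula with 3 years of follow-up per patient gives 78.8%; the two-proportion formula gives 82.6%. The stated 80% lies between them.

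**How many patients could be directed.** Section 12.3 taken alone gives 0, because it has no same-arm rule. Applying the synopsis clause to the enrolment figures gives two upper bounds:
- Only slots above the planned 74 count as replacements: 78 − 74 = 4, and 4/78 = 5.1%. If all fell in one arm, enrolment would be 41:37.
- Every patient above 70 counts as a replacement: 78 − 70 = 8, and 8/78 = 10.3%. If all fell in one arm, enrolment would be 43:35.

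**Type I error.** The simulation used 35 per arm, exponential survival with 3-year OS 58.8% in both arms, and a one-sided 2.5% log-rank test. Assumptions: censoring uniform between 3 and 4 years after metastasectomy, interim look ignored, and each directed slot equally likely to fall in either arm. Selection is represented by giving selected patients an assumed 3-year OS of 75% to 88.7%. The upper value equals the whole design effect, so it is an upper bound on selection. There were 40,000 trials per cell, so the simulation error is about √(0.03 × 0.97 / 40,000) = 0.0009, or 0.1 point.

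| Situation | 4 directed | 8 directed |
|---|---|---|
| No selection | 2.5% | 2.5% |
| Selection for slots in both arms | 2.5–2.6% | 2.5–2.6% |
| Selection for Arm B slots only | 3.0–3.6% | 3.7–5.0% |

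Selection for Arm A slots only works in the opposite direction and makes the test conservative.

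**What an exact 35/35 split is worth.** The efficiency loss with n1 and n2 resected is 1 − 4·n1·n2/70² = (n1 − n2)²/4900.
- All 4 unresected in one arm of 37/37: resected 33/37, loss 16/4900 = 0.33%.
- All 8 unresected in one arm of 39/39: resected 31/39, loss 64/4900 = 1.31%.
- On average, with non-resection equally likely in each arm (assumption), the expected squared difference equals the number unresected: 4/4900 = 0.08% and 8/4900 = 0.16%.

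Power at the most unequal splits, by the two-proportion formula, is 82.7% (31 control, 39 experimental) and 81.6% (39 control, 31 experimental), against 82.6% at 35/35. In the log-rank simulation with 3–4 years of follow-up, power moves by −1.1 to +0.4 points. A smaller simulation (6,000 trials, exactly 3 years of follow-up) gives 85.0% and 82.2% for the same two splits, against 84.3%.

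**The case against.** The strongest reply is that the plan already settles the matter. An additional patient is a subject. Section 4 requires every subject to be randomised before treatment, and Section 4.1 sets 1:1 without exception. Section 12.3 deals with non-resection through enrolment numbers, and Section 5.1.3 mentions no replacement. One loosely worded synopsis clause is the only outlier, and even it uses the word *randomized*, so ordinary allocation may be all that was meant.

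Much of this stands. A reader might infer that the documents leave the allocation of additional patients undefined. They do not: Sections 4 and 4.1 cover those patients, though without naming them. A reader might also infer that Section 12.3 itself creates up to 4 directed patients. It creates none; 4 and 8 appear only when the synopsis clause is laid over its enrolment figures.

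The reply also notes, correctly, that the inflated error rates need a chain of conditions: the literal clause is put into practice, a site knows that its next patient fills a directed slot, it selects on prognosis, and it does so for Arm B alone. Registration is central, and the documents do not say whether sites would be told of such a slot. Eligibility criteria also limit the choice of patient.

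What the reply does not remove is the contradiction. The clause is current text, it concerns how patients in the primary comparison get their arm, and followed literally it gives a different result from Section 4.1.

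**Conclusion.** The inconsistency is real and should be corrected; its consequence is small and conditional. At most 4 or 8 of 78 patients could be affected, and none if Section 12.3 is followed alone. Power is essentially unchanged, and type I error stays at 2.5% without selection of candidates.

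A reader might go further and infer that the trial is not properly randomised or that its error rate is inflated. The documents support neither. Averages of 3.0–3.6% (4 directed) and 3.7–5.0% (8 directed) arise only if sites know of directed slots and select for Arm B alone. The survival of selected patients, 75% to 88.7% in place of 58.8%, is an assumption made to size that risk. The plan does not state it.

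**What to change.** Delete the last four words of the synopsis clause, those that name the arm. State there, with a cross-reference to Section 4.1, that every additional patient is randomised 1:1 by the same procedure as all other patients. Leave the enrolment rule in Section 12.3 (74, up to 78) as it is.

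This is one deletion and one added sentence; the sample size does not change. The price is that resected numbers may differ slightly between arms, with an efficiency loss of about 0.1–0.2% on average and at most 1.3%. Section 4.1 does not say whether the sequence is blocked. Any chance imbalance from that source exists with or without the clause and is not a cost of this change.

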12.8 Interim Analysis

The total expected number of deaths is 22 at the end of the follow-up period. A single interim analysis is planned after 14 deaths occur. The purpose of this analysis is to allow an early assessment of efficacy. We shall use a Hwang-Shih-DeCani group-sequential boundary with $\gamma = -4$, yielding an O'Brien-Fleming-like α spending function and a one-sided stopping boundary (30). We expect to spend approximately 0.0052 of the total of $\alpha = 0.025$ at the interim analysis and the remaining 0.0198 at the final analysis. Thus the p-value in the interim must be less 0.0052 to conclude that the two arms are significantly different. At the final analysis the p-value would need to be less than 0.0198 for the two arms to be significantly different.

Power calculations were carried out using Version 1.0 the “gsDesign” package in the R statistical system (R language and environment for statistical computing, R Foundation, Vienna, Austria).

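### The single efficacy interim has two unreconciled triggers, 2.5 years and 14 deaths, and its fixed 0.0052 threshold follows the declared spending function only near 14 of 22 deaths

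*Combined protocol and SAP*

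**What the plan says.** The synopsis (Statistical Considerations) states "An analysis is planned at 2.5 years" and adds "The purpose of this analysis is allow an early assessment of efficacy". It gives no death count, no threshold, and no origin for the 2.5 years.

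Section 12.8 states "A single interim analysis is planned after 14 deaths occur", for the same purpose, against this background: "The total expected number of deaths is 22 at the end of the follow-up period". It names the method ("We shall use a Hwang-Shih-DeCani group-sequential boundary with" gamma = -4, one-sided) and the spend: "We expect to spend approximately 0.0052 of the total of" alpha = 0.025. It then fixes both decision rules: "Thus the p-value in the interim must be less 0.0052 to conclude that the two arms are significantly different", and "At the final analysis the p-value would need to be less than 0.0198 for the two arms to be significantly different".

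No section says which trigger governs, presents 2.5 years as the expected date of the 14th death, or says that the boundaries will be recalculated if the look falls at another count.

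**The concern.** The two statements share a purpose, and Section 12.8 says there is one interim. They therefore read as two triggers for the same look. The missing origin matters because overall survival in the primary analysis runs from metastasectomy, some months after randomization.

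An alpha-spending boundary is a function of the information available at the look, here deaths divided by 22. A date does not fix that quantity. If the look is taken by date and judged against 0.0052, the threshold no longer matches the function the plan declares. The monitoring committee, which is to receive data on the stopping rules (Section 13.2), would have two candidate times for one rule. With only 22 deaths expected in total, one or two deaths change the boundary appreciably.

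**Working it through.** **Inputs from the documents.** 35 resected patients per arm; 3-year survival 58.8% and 88.7%; one-sided 2.5% log-rank test (Section 12.3). Estimated accrual 12 months (synopsis). Interim at 14 of 22 deaths, Hwang-Shih-DeCani with gamma = -4, thresholds 0.0052 and 0.0198 (Section 12.8). Four two-week cycles, then surgery about 4 weeks later; the experimental arm starts 28 days earlier (Sections 5.1.2 and 5.1.3).

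**Assumptions added here.** Exponential survival, uniform accrual, and no censoring other than end of follow-up. The time from enrolment to surgery is set either to zero or to 3 months (control: 8 + 4 = 12 weeks) and 4 months (experimental: 12 + 4 = 16 weeks).

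**1. The plan's own figure.** The spending function is alpha(t) = 0.025 × (exp(4t) − 1)/(exp(4) − 1), with t = deaths/22 and exp(4) − 1 = 53.60.

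At 14 deaths, t = 0.636, exp(4t) = 12.75, and alpha = 0.025 × 11.75/53.60 = 0.0055. The stated 0.0052 corresponds to t = 0.624, or 0.624 × 22 = 13.7 deaths. Unrounded counts would explain the gap (14/22.4 = 0.625 gives 0.0052), and the plan calls the spend approximate.

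**2. Spend at other counts, and overall alpha with the written pair.** Overall alpha is the chance, with no treatment effect, of p < 0.0052 at the interim or p < 0.0198 at the final. It comes from a bivariate normal with correlation √t.

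| Deaths at look | Declared spend | Overall alpha with 0.0052 and 0.0198 |
|---|---|---|
| 8 | 0.0015 | 0.0232 |
| 11 | 0.0030 | 0.0225 |
| 13 | 0.0045 | 0.0219 |
| 14 | 0.0055 | 0.0217 |
| 16 | 0.0081 | 0.0211 |
| 18 | 0.0118 | 0.0205 |

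The last column stays below 0.025 throughout. It must: 0.0052 + 0.0198 = 0.025, so the Bonferroni bound holds at any interim timing.

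**3. Expected deaths at 2.5 years.** Yearly hazards are −ln(0.588)/3 = 0.1770 and −ln(0.887)/3 = 0.0400. Expected deaths per arm are 35 × the mean of 1 − exp(−hazard × follow-up) over the accrual period.

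| Reading of 2.5 years | Expected deaths | Declared spend at that count |
|---|---|---|
| From first enrolment, no surgery lag | 10.4 + 2.7 = 13.1 | about 0.0046 |
| From first enrolment, 3- and 4-month lag | 9.3 + 2.3 = 11.5 (unrounded sum) | about 0.003 |
| 2.5 years of follow-up for each patient | 12.5 + 3.3 = 15.8 | about 0.008 |
| From end of accrual, with and without lag | 17.0 to 18.3 | about 0.010 to 0.012 |

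Fourteen deaths are expected at month 32 without the lag and month 35 with it. If both arms died at the control rate, month 30 from first enrolment would give about 18 to 21 deaths, close to the planned total of 22.

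**4. Final threshold.** 0.0198 is 0.025 − 0.0052, the alpha left to spend. It is not the nominal p-value that spends it, because the two test statistics are correlated. After a look at 14 of 22 with the declared spend of 0.0055, the final p-value threshold that brings the overall level to 0.025 is about 0.0232.

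**The case against.** The best defence is that 2.5 years was meant as a projected date. Counted from first enrolment with no surgery lag, the plan's figures give 13.1 deaths at month 30 and 14 at month 32, a gap of one death and two months. The synopsis gives no threshold; 0.0052 appears only in Section 12.8, beside the 14-death trigger it nearly fits. On that view the statistical section is coherent and the synopsis is a loose summary. This is plausible and limits the seriousness of the point. It does not remove it, because the documents never state that reading, and every reading of 2.5 years computed here misses 14 expected deaths, in both directions.

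A reader might also infer that an off-schedule look inflates type I error. The plan does not support that: the written pair cannot exceed 0.025. A level of 0.0264 arises only if 0.0052 is used at 8 deaths together with a final threshold of 0.0232. The plan does not contain that threshold, and it belongs to a look at 14 deaths; after a look at 8 with the declared spend, the corresponding value is 0.0242. Nor does anything in the documents suggest an intention to time the look by the accumulating data. Two triggers leave room for that doubt; they are not evidence of it.

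**Conclusion.** The inconsistency is real and should be corrected. One efficacy interim has two triggers that the documents do not link, and the threshold attached to it fits the declared function only at about 13.7 of 22 deaths. Under the readings considered, expected deaths at 2.5 years run from about 11.5 to 18, where the declared spend runs from about 0.003 to 0.012. A calendar look held to 0.0052 would therefore be too lenient with fewer deaths and too strict with more.

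The cost is an ambiguous stopping rule and a boundary that departs from its stated basis, not a loss of error control: overall one-sided alpha with the written thresholds is about 0.0205 to 0.0232 for looks at 8 to 18 deaths. The written pair is in fact slightly conservative, about 0.0217 at 14 deaths.

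The death counts rest on exponential survival at the design rates and uniform 12-month accrual. The spends and alpha levels need only the stated function, a total of 22 deaths and the usual normal approximation for the log-rank statistic.

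**What to change.** Make 14 deaths the only trigger in both the synopsis and Section 12.8. Delete 2.5 years from the synopsis, or label it the projected date of the 14th death and state when the clock starts.

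In Section 12.8, state that both the interim and the final boundary are computed from the Hwang-Shih-DeCani function (gamma = -4) at the number of deaths actually observed. For a look at exactly 14 of 22, give about 0.0055 and 0.0232 as illustrative values in place of 0.0052 and 0.0198. Both boundaries need recomputing: replacing only the final threshold while keeping a fixed 0.0052 at an early look would lose the protection the present pair gives.

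The cost is one sentence in the synopsis and a few in Section 12.8, with no change to sample size, visits or data collection.
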